STUDY TREATMENT	
Carfilzomib will be administered intravenously (IV), using the same method, dose level and frequency as administered in the last cycle of the subject's previous carfilzomib study; carfilzomib doses will be administered on Days 1, 2, 8, 9, 15, and 16 of a 28-day cycle (or the same dose level and frequency as administered at the last visit of the prior carfilzomib study) until disease progression and discussion with the Onyx Medical Monitor, diagnosis of new malignancy, unacceptable toxicity, Investigator discretion, voluntary withdrawal, or commercial availability of carfilzomib. Each dose will consist of Carfilzomib for Injection administered on a mg/m² basis. Subjects with a body surface area (BSA) > 2.2 m² will receive a dose based upon a 2.2 m² BSA. Dosing will be continued or modified based upon clinical and laboratory findings.
 
Decreased carfilzomib dosing frequency to include dosing on Days 1, 2, 15 and 16 (eg, every other week dosing schedule), will be permitted at the discretion of the Investigator; the Onyx Therapeutics Medical Monitor may be consulted as needed. Carfilzomib dose reductions for toxicity, to a minimum dose of 11 mg/m², will be permitted following discussion with the Medical Monitor, as needed. Missed doses of carfilzomib will not be made up.
 
Dose escalations above the original dose level are permitted.
 
For subjects with evidence of disease progression, the Onyx Medical Monitor must be consulted prior to the dose escalation or termination from study.
 
Acyclovir or valacyclovir should be given to all subjects with a history of herpes simplex or zoster, per institutional prophylaxis guidelines, unless contraindicated.

PRIMARY ENDPOINT	
• Safety
SECONDARY ENDPOINTS	
• Overall Survival (OS)• Progression Free Survival (PFS)• Time to Progression (TTP)

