7.6 CYCLE 3 AND EVERY 3 CYCLES (DAY 1)

The following assessments must be completed on Cycle 3 and every 3 cycles (Day 1):

1. Serum chemistry – basic panel (Chem 7 or 8), pre-dose; laboratory values must be reviewed prior to dosing.
2. CBC and platelet count, pre-dose; laboratory values must be reviewed prior to dosing.
3. Perform Disease Assessments, ie, extent of disease measurements (per method employed in previous protocol); and response category (see [Appendix D–E](#)).
Note: If disease assessments, per standard institutional practices, occur more frequently than every 3 months (eg every month or every 2 months), the most recent assessment may be reported.
4. *Administer carfilzomib dose IV*
5. Record peripheral neuropathy AEs (all grades)

6. Record Grade 3 and 4 AEs, and all SAEs
7. Record AE (any Grade) leading to a missed carfilzomib dose, carfilzomib dose reduction, or discontinuation. In the event of a toxicity leading to a dose reduction or discontinuation, pertinent laboratory measurements and concomitant medications will be collected and monitored as unscheduled visits.
8. Record any concomitant chemotherapy agents

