8 STUDY DISCONTINUATION

Subjects may withdraw from the study at any time. Subjects who discontinue from the study will be monitored for AEs as described in [Appendix C](#) (NCI-CTCAE Version 3.0).

The Sponsor, Onyx Therapeutics, Inc. may elect to discontinue the study at any time.

The Investigator may remove a subject from the study for the following reasons:

- Noncompliance with study procedures
- Need of treatment with medications not allowed by the study protocol
- Subject no longer consents to participate in the study
- Intercurrent illness that interferes with study assessments
- Incidence or severity of AEs in this study indicates a potential health hazard to the subject
- Confirmation of PD, and discussion with the Medical Monitor

Onyx Therapeutics or designee must be notified within 24 hours if a subject is withdrawn from the study.

If the reason for withdrawal is the occurrence of an AE, the subject will be followed by the Investigator until such events resolve, stabilize, and, according to the Investigator's judgment, there is no need of further follow-up. The reason for withdrawal from the study will be documented in the CRF.

If a subject is withdrawn for PD, the date of the laboratory test or procedure indicating disease progression will be used as the date of PD. The CRFs must have appropriate source

documentation to demonstrate that a subject has progressed. Bone marrow aspirate or biopsy samples for cytogenetic analysis are optional for all MM subjects who discontinue due to PD.

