APPENDIX A: SCHEDULE OF EVENTS

Visit	Screening (Day -30 to -1)	Cycle 1	Every Cycle	Cycle 3 and Every 3 Cycles	End of Study (Within 30 days of last dose of study drug)
Written Informed Consent	X				
Inclusion/Exclusion Criteria	X				
Obtain Previous PX-171 Protocol Unique Identifier	X				
Pregnancy Test ¹	X				
Routine Physical Examination	X				X
Height, Weight, and BSA ²	X		Day 1		
ECOG Performance and Neuropathy Grade	X				
Bone Marrow Sample for Cytogenetics and FISH ³	X				X
CBC + Platelet Count and Serum Chemistry ⁶		Day 1	Day 1	Day 1	
Carfilzomib Dosing (the same dose level and frequency as administered at the last visit of the prior Onyx study)		Days 1, 2, 8, 9, 15, 16, or same dose level and frequency as prior study	Days, 1, 2, 8, 9, 15, 16, or same dose level and frequency as prior study	Days, 1, 2, 8, 9, 15, 16, or same dose level and frequency as prior study	
Disease Assessments (Extent of disease measurements and response), per method employed in previous protocol ⁴	X			Day 1	X
Peripheral Neuropathy AEs (all Grades)	X	X	X	X	X
Grade 3 and 4 AEs, SAEs or AEs Resulting in Missed Dose or Dose Reduction (all Grades) ⁵	X	X	X	X	X
Record any concomitant chemotherapy reagent	X	X	X	X	X

1 Females of childbearing potential must have a negative serum or urine pregnancy test, with a sensitivity of at least 50 mIU/mL, within 3 days prior to dosing.

2 Height done at screening visit only; BSA calculated Day 1 of every cycle. However, dose adjustments not needed for weight gains/losses of $\leq 20\%$.

3 Screening bone marrow aspirate or biopsy for cytogenetics and FISH is optional and is for MM subjects whose disease status at study entry is PR or less. A Bone marrow sample is also optional for all MM subjects at the end of study if there is evidence of disease progression.

4 If disease assessments are done previously within 30 days of first dose of extended study drug, they will not be required again at screening. If disease assessments per standard institutional practices occur more frequently than every 3 months (eg, every month or every 2 months), the most recent assessment may be reported.

5 Record all AEs leading to missed dose, dose reduction or discontinuation. Record all Grade 3 and 4 AEs from time of consent through 30 days post last administered dose of study drug or initiation of a new anti-cancer therapy.

6 CBC + Platelet Count and Serum Chemistry data will not be routinely recorded on CRFs.

**Appendix B: ECOG Performance Scale

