APPENDIX E: RESPONSE CRITERIA FOR SOLID TUMORS

Evaluation of Target Lesions	
Complete Response (CR):	Disappearance of all target lesions
Partial Response (PR):	At least a 30% decrease in the sum of the LD of target lesions, taking as reference the baseline sum LD
Progressive Disease (PD):	At least a 20% increase in the sum of the LD of target lesions, taking as reference the smallest sum LD recorded since the treatment started or the appearance of one or more new lesions
Stable Disease (SD):	Neither sufficient shrinkage to qualify for PR nor sufficient increase to qualify for PD, taking as reference the smallest sum LD since the treatment started
Evaluation of Non-Target Lesions	
Complete Response (CR):	Disappearance of all non-target lesions and normalization of tumor marker level
Incomplete Response/ Stable Disease (SD):	Persistence of one or more non-target lesion(s) or/and maintenance of tumor marker level above the normal limits
Progressive Disease (PD):	Appearance of one or more new lesions and/or unequivocal progression of existing non-target lesions ¹

¹ Although a clear progression of “non target” lesions only is exceptional, in such circumstances, the opinion of the treating physician should prevail and the progression status should be confirmed later on by the review panel (or study chair).

Evaluation of Best Overall Response

The best overall response is the best response recorded from the start of the treatment until disease progression/recurrence (taking as reference for PD the smallest measurements recorded since the treatment started). In general, the subject's best response assignment will depend on the achievement of both measurement and confirmation criteria.

Target Lesions	Non-Target Lesions	New Lesions	Overall Response
CR	CR	No	CR
CR	Incomplete Response/SD	No	PR
PR	Non-PD	No	PR
SD	Non-PD	No	SD
PD	Any	Yes or No	PD
Any	PD	Yes or No	PD
Any	Any	Yes	PD

- Subjects with a global deterioration of health status requiring discontinuation of treatment without objective evidence of disease progression at that time should be classified as having “symptomatic deterioration.” Every effort should be made to document the objective progression even after discontinuation of treatment.

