5.2 Study Day

Study Day represents the elapsed number of days from Study Day 1, inclusive. Unless otherwise specified, the timing of all study-related events, assessments, and interventions will be calculated relative to Study Day 1. If assessment date is after date of study day 1, study day will be calculated as:

$$\text{Study Day } n = (\text{Date of assessment} - \text{Date of Study Day 1}) + 1 \text{ day}$$

If assessment date is before date of study day 1, study day will be calculated as:

$$\text{Study Day } -n = \text{Date of assessment} - \text{Date of Study Day 1}$$

5.3 Cycle 1 / Cycle Day 1

The first 28-day treatment cycle will begin with the first dose of carfilzomib, and will be denoted as “Cycle 1 / Cycle Day 1”. In general, the start date of each cycle (i.e., Cycle Day 1 of Cycle k , where $k=1$ to last cycle) equals the date of the first dose of carfilzomib administered in the corresponding cycle. If carfilzomib is permanently discontinued,

then the cycle and cycle day for study-related assessments done after the last cycle of carfilzomib will be replaced in the tables, figures, and listings with the visit label (e.g., end of study assessment). The visit date and study day also will be used to identify the timing of such assessments.

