7.7.2 Progression Free Survival (PFS)

PFS is defined as number of days between start of treatment and first evidence of documented disease progression or death (due to any cause), whichever occurs first. Disease progression will be determined by the local investigator for regimens with the same baseline using the International Uniform Response Criteria ([Durie et al. 2006, with corrections](#)) (IMWG-URC) for multiple myeloma subjects and RECIST criteria ([Therasse et al. 2000](#)) for solid tumor subjects. PFS will be re-calculated whenever the baseline is reset due to addition of new anti-cancer therapy or increase of carfilzomib dose/frequency:

- 1) For regimens that continue from initial study without baseline being reset, if subjects didn't progress before PX-171-010, then PFS for the period from initial study to PX-171-010 study will be calculated as Disease Progression /Death Date – Date of first dose in initial study + 1 day, and PFS for the period of PX-171-010 study only will be calculated as Disease Progression /Death Date – Date of first dose in PX-171-010 + 1 day.
- 2) For regimens that start in PX-171-010 study with baseline being reset from initial study or previous regimens, PFS will be calculated as Disease Progression /Death Date –

Date of first dose in the first regimen among the regimens with common baseline + 1 day.

PFS will be right-censored for subjects who met one of the following conditions: 1) no baseline disease assessments or any post-baseline assessments, 2) alive and does not have documentation of disease progression before a data analysis cutoff date. The PFS censoring rules are described in Table 1.

Table 1. Censoring Rules for PFS Analysis

Situation	Date of Progression or Censoring	Outcome
No baseline disease assessments or any post-baseline assessments	Date of first dose	Censored
Alive and without documentation of disease progression	Date of last disease assessment	Censored
Death or disease progression between planned disease assessments	Date of death or first disease assessment showing disease progression, whichever occurs first	Progressed
Death or PD immediately after more than 1 consecutively missed disease assessment visit*	Date of last disease assessment before the first missed visit	Censored
Death before first disease assessment	Date of death	Progressed

* If death or PD is more than 168 days after previous disease assessment, or the first dosing date if there is no previous disease assessment.

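### Sites that assess every one or two months need not report the assessment that first shows progression, so PFS and TTP can be dated late for subjects who progress and stay on study

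*Protocol*

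**What the plan says.** - **Reporting.** Protocol Section 7.6 asks for a disease assessment on Day 1 of Cycle 3 and of every third cycle after it. A note adds that if local practice is more frequent, "the most recent assessment may be reported". Appendix A footnote 4 repeats this and gives monthly and two-monthly assessment as examples.
- **Analysis date.** SAP Section 7.7.2, Table 1, dates a PFS event between planned assessments as "Date of death or first disease assessment showing disease progression, whichever occurs first". SAP Section 7.7.3 runs TTP to the first documentation of progression. Protocol Section 10.4.2 likewise runs durations to the first documentation in the extended trial.
- **Data source.** SAP Section 7.7 bases efficacy on the investigator's assessment as entered on the CRF.
- **Dating at withdrawal.** Protocol Section 8 says that "the date of the laboratory test or procedure indicating disease progression will be used as the date of PD", but the sentence opens with the condition that the subject is withdrawn for PD.
- **Staying on after progression.** The Protocol Synopsis (Study Treatment) says: "For subjects with evidence of disease progression, the Onyx Medical Monitor must be consulted prior to the dose escalation or termination from study". Section 1.5 offers escalation to subjects whose disease progresses, and Section 6.4.2 allows added antitumour agents when progression is a concern. SAP Sections 5.5, 7.7.2 and 7.7.3 provide for these subjects by resetting baseline and recalculating PFS and TTP.

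**The concern.** The analysis needs the earliest assessment that met progression criteria. The reporting note does not make sites supply it. A site that assesses monthly can follow the note exactly and send one result per 3-cycle visit, leaving up to two earlier results out of the only data source the SAP uses.

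For a subject withdrawn for PD this does little harm, because Section 8 ties the date to the test itself. For a subject who progresses and continues, no equivalent instruction covers what goes on the CRF. These are also the subjects whose PFS and TTP the SAP splits by regimen, so the date that closes the earlier regimen matters.

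Both possible errors, a late date and a lost event, lengthen PFS and TTP. Both depend on how a site chooses to report, not on the disease.

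**Working it through.** The plan states no figure for this and has no power calculation to reproduce. The check is of the reporting grid.

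**Inputs**
- Cycle length is 28 days: "The first 28-day treatment cycle will begin with the first dose of carfilzomib" (SAP Section 5.3).
- Reporting visits are Day 1 of Cycles 3, 6, 9 and so on (Protocol Section 7.6).
- Assessment is every month or every 2 months (Appendix A footnote 4), taken here as 28 or 56 days, timed from first dose. That timing is an assumption.

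**Grid.** The first visit falls 2 × 28 = 56 days after first dose. Later visits are 3 × 28 = 84 days apart, at days 140, 224, 308 and 392. The SAP's 168-day missed-assessment window equals 2 × 84, which agrees with this grid.

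**Delay** = day of the assessment reported − day of the first assessment showing PD, if PD persists and only the latest result is sent.

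| Window (days after first dose) | Assessments | Delay (days) | Mean if equally likely |
|---|---|---|---|
| First, monthly | 28, 56 | 28, 0 | 14 |
| Each later one, monthly | e.g. 84, 112, 140 | 56, 28, 0 | (56 + 28 + 0)/3 = 28 |
| Later, two-monthly | 112 (reported at 140); 168, 224 (224 reported at 224) | 0; 56, 0 | (0 + 56 + 0)/3 = 18.7 |

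**Equal-chance assumption.** Suppose instead that time to PD is exponential with median m days, and let q = 2^(−28/m). The first PD-positive assessment then falls at positions 1, 2 and 3 of a full window in the ratio 1 : q : q². The mean delay is (56 + 28q)/(1 + q + q²). Medians of 3, 6 and 12 months (at 30.4375 days per month) are assumptions, not from the documents.
- 3 months: q = 0.809, mean 31.9 days
- 6 months: q = 0.899, mean 30.0 days
- 12 months: q = 0.948, mean 29.0 days

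For the first window the mean is 28/(1 + q), which gives 15.5, 14.7 and 14.4 days. The result is not sensitive to the equal-chance assumption.

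**Lost event (illustration).** PD is first met at day 84, the regimen is changed, and the day-140 assessment no longer shows PD. If only day 140 is reported, the CRF holds the results at days 56 and 140, neither showing PD. Under SAP Table 1 a living subject without documented progression is censored, so the event that ended the earlier regimen disappears.

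**The case against.** The case against has five parts.

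1. **The note is permissive.** It can be read as letting a recent local assessment stand in for the visit assessment, as the screening waiver in the same footnote does. A reader might infer that sites are told to send only the latest result or to hold back an earlier progression. The text does not say so. It also does not require the earlier result, and the gap rests on that.

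2. **Section 8 is not the only dating rule.** This is correct. Protocol Section 10.4.2 and SAP Table 1 set the analysis date for every subject, withdrawn or not. It would be wrong to infer that continuing progressors have no defined event date. What is missing is a rule that puts the date on the CRF.

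3. **Other records exist.** The Medical Monitor is consulted, a regimen-change CRF records reasons (SAP Section 7.4), and the baseline reset presupposes measurements at the time of change. These may flag progression. The documents do not say that any of them captures the date of the first assessment meeting the criteria. The CRF itself is not available here, so it may already do so.

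4. **The reported date is no later than the protocol's own minimum schedule would give.** This is fair for late dating: a subject assessed only every 3 cycles would have the same date. But the SAP asks for the first assessment showing progression among those performed, and the argument does not cover an event that is lost.

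5. **The stakes are low.** PFS and TTP are secondary, the study has a single arm and no hypothesis is tested. This limits the priority of the point.

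A further inference is tempting for solid tumours. Appendix E judges progression "taking as reference the smallest sum LD recorded since the treatment started", so an unreported nadir might seem to raise the reference and delay PD further. The documents do not support this. SAP Sections 7.7, 7.7.2 and 7.7.4.1 leave progression and best response to the local investigator, who has every local value whether or not it reaches the CRF.

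**Conclusion.** The point holds as a gap in CRF capture. A site that follows Section 7.6 as written can leave out the assessment that first met progression criteria. For subjects who progress and stay on study, no instruction ensures that its date is recorded.

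Under monthly assessment the delay is 0, 28 or 56 days in a full 84-day window, and 0 or 28 days in the first window. The 28-day mean is an upper-end figure. It assumes that sites use the allowance fully, that the three positions are equally likely, that PD persists to the reported assessment and that nobody is withdrawn for PD. It should not be read as the expected shift in the study's median PFS. The documents do not say how many sites assess this often or how many subjects progress and continue. In the less common case, where the latest assessment no longer shows PD, the event is replaced by censoring.

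The SAP plans Kaplan-Meier quartiles with 95% confidence intervals by cohort and regimen, and these dates feed them directly. The change is worth making because it costs little, although the endpoints are secondary and descriptive.

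**What to change.** 1. In Protocol Section 7.6 and Appendix A footnote 4, add after the existing note: *except that the first assessment meeting progression criteria must be reported with its own date.*
2. In Protocol Section 8, make the PD dating sentence apply to every documented progression, whether or not the subject is withdrawn.

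No requirement to report nadir or best response is needed for this purpose. The change affects reporting only and leaves visits, tests and treatment rules as they are. The cost is protocol wording and one or two extra CRF entries per affected subject. If the CRF already collects this date, the change only puts existing practice in writing.

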7.7 END OF STUDY ASSESSMENTS (WITHIN 30 DAYS OF STUDY DISCONTINUATION)

The following assessment must be completed within 30 days of administration of last dose of study drug and prior to initiation of any new therapy:

1. Perform complete physical examination
2. Perform Disease Assessments, ie, extent of disease measurements (per method employed in previous protocol); and response category (see [Appendix D–E](#)).
3. OPTIONAL: Bone marrow aspirate and/or biopsy for cytogenetic and FISH analysis (only required for *MM* subjects whose reason for study discontinuation is PD).
4. Record peripheral neuropathy AEs (all grades)
5. Record Grade 3 and 4 AEs, and all SAEs
6. Record any concomitant chemotherapy agents

7.8 TUMOR RESPONSE ASSESSMENT

Efficacy Measures

Tumor measurements and efficacy assessments will be in accordance with the methods employed in the subject's prior carfilzomib study. For subjects participating in a carfilzomib trial without prior tumor measurements and efficacy assessments (eg, PX-171-008), tumor assessments will be conducted at the time of screening for the current study using the appropriate method (eg, RECIST criteria for solid tumors); these assessments will be used as the subjects' baseline disease assessments for determining response and progression while on the current Protocol (PX-171-010). Disease assessments (eg, Extent of Disease Measurements and objective response category) will occur within 30 days prior to enrollment to determine eligibility, at least every 3 months throughout study participation, and at end of study. Subjects will be evaluated for disease response according to the parameters employed in their previous carfilzomib study. Refer to [Appendix D–E](#) for Response Criteria.

7.9 CORRELATIVE STUDIES

7.9.1 CYTOGENETIC AND FISH STUDIES

A bone marrow biopsy and/or aspirate for determining percent plasma cell involvement, including metaphase cytogenetic and FISH studies are optional for all MM subjects entering with a PR, MR, or SD. Samples for cytogenetic and FISH analysis will also be optional for all MM subjects who discontinue study due to PD. Bone marrow cytogenetic and FISH analyses will be carried out at the site's local laboratory, per standard of practice, or in a Central Reference Laboratory.

